3.1 Definition of Baseline

For the endpoints based on daily recordings in the eDiary, i.e. the migraine, headache, aura without headache and acute migraine medication endpoints, the baseline values will be based on the data recorded daily in the eDiary during the first 28 days following the screening visit.

For the actigraphy endpoints, the baseline values will be based on the data recorded daily by the wearable device during first 28 days following the screening visit.

For all other endpoints, baseline will be defined as the latest available valid measurement taken prior to the administration of IMP.

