3.2 Definition of Trial Periods

Classification of concomitant medications and adverse events into trial periods is defined in Section 8, and Section 12.1, respectively. For other data, assessments from the Withdrawal visit and Unscheduled visits will be assigned to a nominal, i.e. scheduled visit (see Section 15.13).

The trial consists of the following periods:

- Screening Period (28-30 days): Starts at Visit 1 (End of Week -4) and continues until the beginning of Visit 2 prior to administration of the IMP (End of Week 0).
- Placebo-controlled Period (12 weeks): Starts at the beginning of Visit 2 IMP infusion (End of Week 0) and continues until the beginning of Visit 5 IMP infusion (End of Week 12), or, for the participants with no Visit 5 IMP infusion, until Week 12, or, for the participants withdrawn from the study prior to Week 12 visit, until Week 12 (84 ± 2 days after Visit 2 IMP infusion).
- Open-label Period (20 weeks): Starts at the beginning of Visit 5 IMP infusion (End of Week 12) and continues up to and including the Safety Follow-up visit (Week 32).

The definition of the Placebo-controlled Period implies that for participants in the all-participants-treated-follow-up set (APTS-FU), see Section 4 below for definition, adverse events and concomitant medications reported after withdrawal in the Placebo-controlled Period but before Week 12, will be allocated to the Placebo-controlled Period.

For the APTS-FU patients, the safety assessments, and concomitant medications data subsequently collected at the Safety Follow-up visit will be reported separately in data listings.

For patients who enter the Open-label Period, the safety assessments and concomitant medications data collected at the Safety Follow-up visit will be presented together with the safety assessments and concomitant medications data collected during the Open-label Period.

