15.13 Assigning Data to Visits

See Section 3.1 for definition of Baseline.

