15.13.1 BI and SDS:H

With respect to the Brief Educational Intervention (BI), data will be assigned to visits, regardless of the timing of the BI, also in the case the BI was missed. If an observation for SDS:H exist with visit label equal to Visit 2, it will be assigned to Visit 2, also in the case it was done after the Visit 2 date. Similarly, if an observation for SDS:H exist with visit label equal to Visit 5, it will be assigned to Visit 5, also in the case it was done after the Visit 5 date.

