15.13.2 Pharmacoeconomic Assessments (ePROs)

For treated patients withdrawing prior to Week 12, the withdrawal visit will also include efficacy evaluations (PGIC, MBS, HADS, HIT-6, mMIDAS, MSQ, EQ-5D-5L, HCRU, WPAI:M and TSQM-9). These assessments will be assigned to nominal Visit 5.

Using the same principle for participants withdrawing in the open-label period after infusion of the IMP at Visit 5, the ePRO assessments will be assigned to nominal Visit 7.

Unscheduled visits will not contain assessments of the ePROs mentioned above.

ePROs will be summarized based on the following visit assignment rules to be applied for each ePRO endpoint separately:

- If exactly one observation exists for a specific visit label, this should be used.
- If more than one observation exist for a specific visit label the following would apply:
 - Week 4 (Visit 3): Choose the observation closest to Analysis day (ADAY) = 26.
 - Week 12 (IMP Visit 5): If one or more observations exist that are made prior to the IMP infusion at visit 5, choose the one closest to the IMP infusion at visit 5. If no such observation exists, choose the one closest to ADAY = 82.
 - Week 24 (Visit 7): Choose the observation closest to 82 days after the IMP Visit 5 date.
- Any remaining observations that are not assigned to a visit after this procedure, will constitute candidates for assignment to a trial visit using the assignment rules for withdrawals stated above. In case there is any observation on Visit 5/Visit 7 reflecting a planned assessment, this will take precedence over the candidate. In case, no planned assessments are present at Visit 5 or Visit 7 visits, the observation closest to ADAY = 82, or 82 days after IMP Visit 5, respectively, will be chosen. For an observation to be assigned to Visit 7, IMP needs to have been administered at Visit 5.

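### SAP 15.13 lets an ePRO or SDS:H completed after the Visit 5 open-label eptinezumab infusion stand as the Week 12 placebo-controlled value

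*SAP*

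**What the plan says.** **ePROs (SAP 15.13.2).** The first rule carries no timing condition: "If exactly one observation exists for a specific visit label, this should be used". Timing matters only when several forms share the Week 12 label. The rule then reads "If one or more observations exist that are made prior to the IMP infusion at visit 5, choose the one closest to the IMP infusion", followed by the fallback "If no such observation exists, choose the one closest to ADAY = 82". The fallback does not exclude forms completed after the infusion and sets no upper limit.

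**SDS:H (SAP 15.13.1).** If a record carries the Visit 5 label, "it will be assigned to Visit 5, also in the case it was done after the Visit 5 date".

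**Period boundary and treatment.** Under SAP 3.2 the Placebo-controlled Period "continues until the beginning of Visit 5 IMP infusion (End of Week 12"). Protocol 6.1 gives both randomised groups eptinezumab 100 mg at that visit.

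**Intended conduct.** Protocol 8.1 requires the Visit 2 and Visit 5 ePROs on site, on the visit date and before the infusion. Protocol 8.5 requires the Week 12 SDS:H before the infusion.

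**Use of the values.** SAP 11.5 compares the groups at Week 12 on HIT-6, mMIDAS, MSQ, EQ-5D-5L VAS, WPAI:M, HADS, TSQM-9 and PGIC by MMRM, and on MBS by ANCOVA. SAP 11.6 analyses SDS:H by ANCOVA as an exploratory endpoint.

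**The concern.** The Week 12 comparison should contrast brief intervention plus eptinezumab with brief intervention plus placebo. Once the Visit 5 infusion has started, a placebo participant is on open-label eptinezumab and knows it. Protocol 1.1.1 describes a preventive effect from the day after the first infusion and relief of ongoing attacks within hours. A late placebo form can therefore reflect active drug, expectation, or both.

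The rules act only when a site or participant departs from the required order, but that is the situation they were written for. In it they admit data that SAP 3.2 places in the Open-label Period. Section 18 of the SAP, which lists changes from the protocol's analyses, does not mention this. At stake is an understated Week 12 difference on the quality-of-life, work-productivity and analgesic-dependence endpoints.

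**Working it through.** **Step 1. Trace the rules for a placebo participant infused at Visit 5.**

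| Records available | Rule | Week 12 value |
|---|---|---|
| One Visit 5 ePRO, before infusion | Single-form rule | Pre-infusion; sound |
| One Visit 5 ePRO, after infusion | Single-form rule | Post-crossover |
| Several, at least one before infusion | Priority rule | Pre-infusion; sound |
| Several, all after infusion | Day 82 fallback | Post-crossover |
| SDS:H labelled Visit 5, done after the infusion on a later date | SAP 15.13.1 | Post-crossover |

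The single-form rule is at least as open as the fallback. If Visit 5 falls in its window (Day 84 ± 2, so Day 82 to 86), every post-infusion form is dated Day 82 or later. The fallback then picks the earliest of them, but that form is still post-infusion.

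**Step 2. Reproduce the plan's own figure.** SAP section 14 gives a difference of 1.5 MMDs, SD 6.2, two-sided 5%, 80% power, 270 per group, and 285 after 5% non-contribution.

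- n per group = 2 × (1.960 + 0.842)² × 6.2² / 1.5² = 268.2, so 269; the plan has 270.
- Power at 270 per group: standard error = 6.2 × √(2/270) = 0.534; 1.5/0.534 = 2.811; Φ(2.811 − 1.960) = 80.3% (80.1% with the noncentral t).
- 270/0.95 = 284.2, so 285 per group and 570 in total.

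The figures reproduce. They concern a diary endpoint that these rules do not touch, so the fix does not change the sample size.

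**Step 3. Size of the dilution.** The documents give no rate of late forms, so this is a range under assumptions. Let f be the fraction of placebo Week 12 values recorded after the infusion and g the share of the eptinezumab effect that they carry. Assume that values in the eptinezumab group do not shift. The placebo mean moves by f × g of the effect, so the estimated difference is multiplied by (1 − f × g).

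The SAP gives no effect size for the ePROs. The power column therefore takes an endpoint with the design's standardised effect (1.5/6.2) and 270 per group: Φ(2.811 × (1 − f × g) − 1.960).

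| f | g | Factor | Power |
|---|---|---|---|
| 0 | – | 1.000 | 80.3% |
| 1% | 1 | 0.990 | 79.5% |
| 5% | 0.5 | 0.975 | 78.2% |
| 5% | 1 | 0.950 | 76.1% |
| 10% | 1 | 0.900 | 71.6% |

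**The case against.** The case for leaving the rules alone is that they handle deviations from a mandatory order of events, that a pre-infusion form already takes priority when several exist, and that the expected bias works against the sponsor's drug. The Day 82 fallback also serves participants who had no Visit 5 infusion, for whom it does no harm. All of this stands and limits the impact. None of it explains why a lone post-infusion form should count as placebo-controlled data.

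The size can also be challenged, and fairly. WPAI:M looks back 7 days, HCRU 4 weeks and mMIDAS 1 month, and PGIC rates change since the Baseline Visit. A form completed hours or a day late mostly covers time before the infusion, so g = 1 is a ceiling.

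The SAP's vital-signs windows (Table 11) do close at the Visit 5 infusion. That is a weak precedent, because vital signs are measured on both sides of the infusion by design. It shows only that the SAP can use infusion start as a cut-off.

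A reader might also infer that the SAP lets a late SDS:H serve as baseline, because 15.13.1 says of a Visit 2 record that "it will be assigned to Visit 2, also in the case it was done after the Visit 2 date". The documents do not support that as a clear permission. SAP 15.13 opens with "See Section 3.1 for definition of Baseline", and 3.1 says that "baseline will be defined as the latest available valid measurement taken prior to the administration of IMP". Section 15.13.1 assigns a visit and does not call the value baseline. Nor does a late SDS:H necessarily follow the brief intervention: the intervention starts with the SDS:H questions, and 15.13.1 itself allows for an intervention that was mistimed or missed. What remains is an ambiguity between two sections, unrelated to crossover, that one sentence would settle.

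**Conclusion.** The point holds for Week 12. Read as written, SAP 15.13.1 and 15.13.2 can place values from after the start of open-label eptinezumab in the randomised Week 12 comparison, in conflict with the period definition in SAP 3.2.

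The reach is limited to secondary ePRO endpoints and the exploratory SDS:H endpoint, and within those to participants whose form was late. A reader might infer that the primary result or the testing hierarchy is exposed. It is not: the primary and all key secondary endpoints come from the eDiary, whose 4-week counts are derived under SAP 15.1, not under these visit-assignment rules.

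The likely direction is toward no difference, provided that late forms in the eptinezumab group do not shift as well. The size depends on two unknowns. Plausible factors run from 0.99 (f = 1%, g = 1) through 0.975 (f = 5%, g = 0.5) to 0.90 (f = 10%, g = 1). A reader might take the dilution to equal the fraction of late forms; that needs g = 1, which the recall periods make an upper bound. This is worth correcting because the rule contradicts the SAP's own boundary and is cheap to repair, not because a large bias has been shown.

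**What to change.** - **SAP 15.13.1 and 15.13.2, Week 12:** for participants infused at Visit 5, use only ePRO and SDS:H values recorded before the start of that infusion. This applies to a lone form as well as to several. Otherwise set the Week 12 value to missing and list the late form with its timing.
- **Sensitivity analysis:** repeat the Week 12 analyses with the late forms included.
- **Day 82 rule:** keep it for participants with no Visit 5 infusion.
- **SAP 15.13.1, Visit 2:** state that an SDS:H recorded after the first infusion is not baseline, in line with SAP 3.1.

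**Cost.** The change needs a few lines of SAP text and a time comparison in the programs. Infusion start times are recorded (SAP section 9), and 15.13.2 already needs form timing relative to the infusion. A few Week 12 values become missing. In the MMRM analyses those participants still contribute Week 4 data where available; in the single-time ANCOVAs for MBS and SDS:H they drop out of the main analysis. The listing would also show how many late forms there were, which the documents do not say.

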15.13.3 Safety Variables

Vital signs

Vital signs will be assessed before and after infusion at nominal visits. For unscheduled or withdrawal visit assessments of vital signs, the values will be assigned a nominal visit according to [Table 11](#) and [Table 12](#).

Table 11 Visit Windows for Placebo-controlled Period – Vital Signs (Pulse rate, Blood Pressure, Temperature)

Nominal Visit Number	Nominal Visit Week	Nominal Visit Day	Time Window
V1 (Screening Visit)	-4	-28	Before day 0 and before first IMP infusion
V2 (Baseline Visit) pre-dose	0	0	Same day as first IMP infusion (Day 0) and prior to IMP infusion on that date
V2 (Baseline Visit) post-dose	0	0	After start of first IMP infusion to day 42
V5 pre-dose	12	84	Day 43 to start of V5 IMP infusion

Table 12 Visit Windows for Open-label Period – Vital Signs (Pulse rate, Blood Pressure, Temperature)

Nominal Visit Number	Nominal Visit Week	Nominal Visit Day	Nominal Visit Day Relative to Visit 5 IMP Infusion	Time Window Relative to Visit 5 IMP Infusion
V5 post-dose	12	84	0	After start of V5 IMP infusion to day 42
V7	24	168	84	Day 43 to the day after the safety follow-up visit

If there is more than one assessment at a visit (either due to multiple assessments or because an unscheduled or withdrawal visit assessment is mapped to a nominal visit with an already existing value) the value that will be used in summary tables by visit will be the one closest to the nominal day for the visit but prioritizing values from scheduled visits above values from withdrawal or unscheduled visits. In the ordering of multiple values, assessments without recorded time will come after assessments with recorded time and the first in the ordering will be picked.

15.14 Missing Data Handling

15.14.1 Headache and Migraine Day

For the primary analysis a headache will be classified as a migraine or non-migraine headache based on available symptoms. If no symptoms are captured for a headache, i.e. no information on symptoms is available for any of the days of the headache, then each day of the headache will not be a reporting day, and it will be prorated.

For evaluations based on daily duration/symptoms for the exploratory analyses: days with missing information on symptoms will be imputed considering all days with information on symptoms available for that headache. If no symptoms are captured for the given day of the headache, then it will be considered a day with migraine, if either of the other days of the headache is a day with migraine; if no symptoms are captured for the given day of the headache,

and if all other days with symptoms are not days with migraine, then this day will also be a day without migraine; if no symptoms are captured for a headache, then each day of the headache will not be a reporting day, it will be prorated.

For participants diagnosed with migraine without aura, it will be assumed that on days for which the aura without headache eDiary is missing, no aura without headache took place.

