9.1.3 Classifications for Eligibility

Fulfilment of criteria for migraine, according to the eligibility criteria in this protocol, will be confirmed via prospectively collected information in the eDiary during the screening period, that is, migraine occurring on ≥ 8 days and headache occurring on ≥ 15 to ≤ 26 days. Prior to randomization, the investigator will review the data in the *eDiary Eligibility Report* to determine if eligibility criteria are fulfilled.

Definition of a Migraine Day: The migraine day definition is based on the IHS guidelines¹ for controlled studies of preventive treatment of migraine in adults and here defined as a day with a headache that:

- lasts at least 30 minutes and meets ICHD-3 criteria C and D for migraine without aura (1.1) (following IHS corporate round table meeting held on 17th December 2021, consensus on changing the duration to 30 minutes for both EM and CM)
- or lasts at least 30 minutes and where the patient had an aura with the headache (migraine with aura)*
- or lasts ≥ 30 minutes and meets two of the three ICHD-3 criteria B (without the condition on 72 hours), C and D for migraine without aura (1.1) (probable migraine**)
- or is a day with a headache that is successfully treated with a triptan, ergotamine, or other migraine-specific acute medication (for this purpose the master medication list will be classified into *migraine-specific* and *non-migraine-specific medication*) ***

Data on characteristics of a headache will be collected in the eDiary for each headache, and for each headache it will be determined if it qualifies as a migraine day.

If a headache lasts ≥ 72 hours, the days will still be counted as *headache days* or *migraine days* as aligned with the IHS guidelines.¹

A day where the symptoms are not recorded for an ongoing headache (missed data entry) will be classified as a headache day.

Further details on the definitions:

- * At the Screening Visit, the patient's usual aura is described. The patient will be asked about occurrence of aura based on questions in the eDiary as follows: "*Did you experience an aura with this headache?*"

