3.6.2 Headache Day

A headache day is defined as a day with a headache that lasts ≥ 30 minutes or that meets the definition of a migraine day.

Note: In case of a headache with start date/time and end date/time spanning multiple calendar days, all the calendar days overlapping with the ongoing headache (regardless of duration) will be counted as a headache day (or a migraine day if the headache qualifies as a migraine headache).

If a headache lasts ≥ 72 hours, the days will still be counted as *headache days* or *migraine days* as aligned with the IHS guidelines.

For the exploratory analyses corresponding to using the alternative definitions 1) and 2) for a migraine day as outlined in the previous section, a headache day is defined as a day on which the headache lasts ≥ 30 minutes on that specific day or that meets the definition of a migraine day.

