3.7 Definition of a Reported eDiary Day and a Missing eDiary Day

A reported eDiary day is a day where at least one of the following pieces of information are available:

- A headache event is reported to take place and the participant has recorded the daily symptoms for at least one of the days spanned by this headache
- The headache eDiary has been completed, and it has been confirmed that no headaches happened on this day
- Aura without headache diary is reported with a taken medication

A missing eDiary day is defined as a day that is not a reported eDiary day.

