15.1.1 Monthly Migraine Days /Monthly Headache Days

The following describes the derivation of MMDs. The derivation of MHDs follows the same principles. Definitions of a migraine day and a headache day are described in Section 3.6.

Pooling of symptoms

To assess whether a headache is a migraine headache, daily reported symptoms will be pooled to assess the migraine criteria described in Section 3.6. The worst reported symptom will be used, for example, if different levels of worst pain have been reported on different days of the same headache, the worst of these levels will be used to assess the migraine criteria.

Regarding successful medication use for the criterion “a headache that is successfully treated with a triptan, ergotamine, or other migraine-specific acute medication”: a medication can only be considered successful if the question *“Did at least one of the medications you took today successfully treat your headache?”* is answered positively on the same day as the medication intake date.

4-Week Intervals

For Baseline and each 4-week period post-baseline in the trial, the number of MMDs will be derived as the number of migraine days within each 28-day interval using the imputation rules described below. The 4-week periods post-baseline that are considered are the following: Weeks 1-4, Weeks 5-8, Weeks 9-12, Weeks 13-16, Weeks 17-20 and Weeks 21-24.

In general, for 4-week periods where the number of reported eDiary days are at least 14 days out of the 28 days, prorating will be used to calculate the MMDs, and for 4-week periods where the number of reported eDiary days are less than 14 days out of the 28 days, the MMDs will be set to missing. Once prorating has been applied, a non-missing 4-week MMD value is considered a valid assessment.

Prorating

Intended to be used for 4-week periods where the eDiary is completed on at least 14 out of the 28 days, the prorating procedure consists of imputing days with missing information with the observed mean number of migraine days in the period as follows:

$$28^*(\text{Reported Migraine Days}/\text{Reported eDiary Days})$$

This imputation rule will also be used for the Baseline value regardless of the number of reported eDiary days in the screening period.

When the number of MMDs have been calculated for a given 4-week period, the result will be rounded to two decimals.

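### Headaches with no symptom entry on any day are treated as missing days for the headache-day count too, which can lower the MHD level and misclassify CM status near 15 days

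*SAP*

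**What the plan says.** SAP 15.14.1 covers headache and migraine days together. For a headache with no symptom information on any of its days, it says "then each day of the headache will not be a reporting day, and it will be prorated". SAP 3.7 agrees: a reported headache makes a reported eDiary day only if "the participant has recorded the daily symptoms for at least one of the days spanned by this headache". SAP 15.1.1 describes the derivation for monthly migraine days (MMD) and adds "The derivation of MHDs follows the same principles", with no exception for this case. Under that section, "the prorating procedure consists of imputing days with missing information with the observed mean number of migraine days in the period". The same prorating is used at baseline, whatever the number of reported days.

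SAP 3.6.2 defines a headache day by a duration of at least 30 minutes, or by meeting the migraine-day definition. For a headache spanning several dates, "all the calendar days overlapping with the ongoing headache (regardless of duration) will be counted as a headache day". SAP 3.6 has start and stop times recorded in the headache diary.

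Protocol 9.1.3 states: "A day where the symptoms are not recorded for an ongoing headache (missed data entry) will be classified as a headache day".

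SAP 3.9.1 makes an MHD of at least 15 the first step of the CM definition and at least 8 MMD the second. MHD is tested in Steps 3 and 4 of SAP 11.2. The composite of fulfilling neither CM nor medication overuse headache (MOH) is tested in Steps 5 and 6.

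**The concern.** Without symptoms a headache cannot be classed as migraine or non-migraine, so treating its days as unknown is reasonable for MMD. For MHD the position differs. If the start and stop times show a headache of at least 30 minutes, the day is known to be a headache day. The rule nevertheless takes it out of both numerator and denominator and fills it in at the participant's average rate, and that average includes the headache-free days.

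Only headache days can be lost by this route, so the missingness depends on the outcome. At stake are the MHD level and, for participants near the threshold, CM status in the Steps 5 and 6 composite. The planned sensitivity analyses would not show the effect. Placebo-based imputation and the tipping-point analysis (SAP 11.3.4) act only on values still missing after prorating, and SAP Table 4 lists no sensitivity analysis for the composite. The alternative migraine-day definitions keep the same rule for a headache with no symptoms at all.

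**Working it through.** The plan states no figure for this point, so there is none to reproduce first.

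**Inputs.** The prorating formula comes from SAP 15.1.1, read for headache days: 28 × (reported headache days / reported eDiary days). The CM threshold of 15 comes from SAP 3.9.1. In one 28-day period let

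- h = headache days with symptom information,
- k = known headache days (at least 30 minutes) made non-reporting because no symptoms were entered,
- m = days missing for any other reason.

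The value of k is an assumption, since the documents give no frequency.

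**Direction.**

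- SAP value: 28h / (28 − m − k).
- Value with the known days counted: 28(h + k) / (28 − m).

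With D = 28 − m, the second minus the first is 28k(D − h − k) / [D(D − k)]. This is never negative, and it is zero only when every one of the D days is a headache day. An enumeration of all 2,030 combinations with k at least 1 and at least 14 reported days agrees: the SAP value is lower in 1,925, equal in 105 and higher in none.

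**Size with m = 0.** If T = h + k is the known number of headache days, the SAP gives 28(T − k)/(28 − k), a loss of k(28 − T)/(28 − k). For k = 1 the loss is 13/27 = 0.48 at T = 15, 8/27 = 0.30 at T = 20 and 2/27 = 0.07 at T = 26.

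| T | k = 1 | k = 2 | k = 3 | k = 4 | k = 5 |
|---|---|---|---|---|---|
| 15 | 14.52 | 14.00 | 13.44 | 12.83 | 12.17 |
| 16 | 15.56 | 15.08 | 14.56 | 14.00 | 13.39 |
| 17 | 16.59 | 16.15 | 15.68 | 15.17 | 14.61 |
| 20 | 19.70 | 19.38 | 19.04 | 18.67 | 18.26 |

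For example, 28 × 14/27 = 14.52 and 28 × 13/25 = 14.56. The first value below 15 occurs at k = 1 for T = 15, k = 3 for T = 16 and k = 5 for T = 17. At T = 20 none of these values crosses the threshold.

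**What a crossing does.** It changes CM status only if MMD is at least 8. Under SAP 15.1.6 it changes the composite only if MOH is also not fulfilled. For Weeks 1-12 (Step 6), the other available periods must also be not fulfilled.

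**Change from baseline.** Take a true fall from 20 to 14, a change of −6.

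- Two symptomless days post-baseline only: 28 × 12/26 − 20 = 12.92 − 20 = −7.08.
- Two in each period: 12.92 − 19.38 = −6.46.
- Two at baseline only: 14 − 19.38 = −5.38.

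The error can go either way.

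**Boundary case.** If these days bring a post-baseline period below 14 reported days, the value becomes missing rather than understated.

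**The case against.** The rule is narrow. A multi-day headache with symptoms on any one day is still counted in full, so most of what Protocol 9.1.3 describes is honoured. That section speaks of a day within an ongoing headache and does not separately address a headache with no symptoms on any day. Its own definition of a compliant diary day also asks for recorded symptoms. Protocol 16.10 leaves further detail on incomplete diary data to the SAP. A reader might infer an undeclared breach of the protocol from the silence of SAP section 18. The documents do not support that; they show a tension between the two texts on a case the protocol left open.

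Such headaches may also be rare. SAP 3.6 requires symptom entry when a headache ends or in the evening routine, diary compliance is checked throughout, and Protocol 16.10 expects mostly sporadic missing data. The affected days are not set to zero: each costs a fraction of a day. A CM change needs a participant at or just above the threshold. All of this stands, and it limits the size of the problem.

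It does not remove the inconsistency inside the SAP. Section 3.6.2 needs no symptoms for a headache day, while 3.7 and 15.14.1 discard the day for want of them.

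**Conclusion.** The point holds for the MHD level and for CM status near the threshold. In both the direction is fixed: MHD is equal or lower, and CM status can move only towards not fulfilled. The figures assume that all other days are reported and that each affected day carries a known headache of at least 30 minutes and no other entry that would make it a reported day.

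A reader might infer that the change in MHD tested in Steps 3 and 4 is biased in favour of eptinezumab. That does not follow. Baseline is lowered by the same rule, the error in change has no fixed sign, and nothing in the documents suggests that symptomless entries differ by arm. Nor does the argument extend to the primary endpoint or Step 2, because migraine status really is unknown without symptoms and prorating MMD is defensible.

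The frequency is not given, so the trial-level effect cannot be calculated and may be small. The correction is still worth making: a stated rule gives a wrong value in identifiable cases, and putting it right costs very little.

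**What to change.** In SAP 3.7 and 15.14.1, separate the reported-day rule for MHD from that for MMD. For MHD and for the first CM step in 3.9.1, at baseline and post-baseline, count the days of any headache with recorded start and stop times and a duration of at least 30 minutes as reported headache days, whether or not symptoms were entered. Keep prorating for MMD.

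Keep the present rule for a symptomless headache whose end time is imputed under 15.14.2. That imputation can extend an unclosed headache to the last evening diary entry, so its later days are not known headache days.

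Report the number of symptomless headache days by arm and period, so that readers can judge the size of the effect.

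No new data are needed. The cost is one additional reported-day flag, and MHD and MMD will then have different denominators in some periods, which the SAP should state.
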